Appendix 1: Protocol Summary

Name of finished/IMP	NA
Name of active substance	NA
Title of trial/trial ID/ EudraCT no.	Incidence of squamous cell carcinoma and other skin neoplasia in subjects with actinic keratosis treated with ingenol disoxate gel 0.018% or 0.037%, or vehicle / LP0084-1369 / EudraCT number: 2017-000228-85
Coordinating investigator(s)	PPD [REDACTED], MD
Sponsor's name/ address	LEO Pharma A/S [name]
Estimated number of trial sites and distribution	Approximately 80 sites in Canada, Germany, France, Italy, Spain, the United Kingdom, and USA
Trial period	Planned First Subject First Visit (FSFV): Q2 2017 Planned Last Subject Last Visit (LSLV): Q4 2019
Main objective(s)	To compare the incidence of SCC after treatment with ingenol disoxate gel and vehicle gel
Methodology	A phase 3 trial to compare the incidence of SCC and other skin neoplasia on skin areas treated with ingenol disoxate gel or vehicle gel for multiple actinic keratosis on face and chest or scalp. The trials is a multi-centre, randomised, open-label, controlled, parallel group, 24-month trial
Number of subjects to be enrolled	No formal sample size calculation has been made. The sample size is determined by the number of subjects who complete Visit 11 in the pivotal phase 3 trials (LP0084-1193, -1194, -1195, -1196) and are willing to enter the extension protocol.
Main criteria for inclusion	
 1. Signed and dated informed consent has been obtained. 2. The subject has been treated in one of the trials LP0084-1193, -1194, -1195, or -1196 and has been evaluated at Visit 11 of that trial.
Main criteria for exclusion	
 1. The subject is in need of treatment with ingenol mebutate or ingenol disoxate in the selected treatment area*. 2. The subject is enrolled in any other interventional clinical trial.

	
For subjects where there is a gap between Visit 11 in one of the trials LP0084-1193, -1194, -1195, or -1196 and participation in the current trial:
 
 1. The subject has been treated with ingenol mebutate or ingenol disoxate in the selected treatment area* after Visit 11 in one of the trials LP0084-1193, -1194, -1195, or -1196 and until participation in the current trial. 2. The subject has been enrolled in any other interventional clinical trial after Visit 11 in one of the trials LP0084-1193, -1194, -1195, or -1196 and until participation in the current trial. 
* The selected treatment area that was documented in the main trial (LP0084-1193, -1194, -1195 and -1196).

IMP(s)	NA
Investigational reference product(s)	NA
Duration of treatment	NA
Main assessments	Adverse events in the treatment area that was documented in the main trials (LP0084-1193, -1194, -1195 and -1196).
Primary endpoint	Time to first squamous cell carcinoma (SCC) in the treatment area
Secondary endpoint(s)	Time to first squamous cell carcinoma (SCC) or other skin neoplasia in the treatment area
Statistical methods	
Data on skin neoplasia from the 14 months observation time in the main trials will be combined with the data from the present trial
 
Primary endpoint: The annual and the 3-year and 2 months cumulative incidence of first event of SCC will be calculated for each treatment group (active and vehicle) using methods of survival analysis in the presence of censoring. The incidence rates will be presented for the event of first SCC as primary endpoint . A proportion hazards model will be fitted if the model assumptions are valid. Log-rank test comparing the two arms will be performed. For descriptive purposes, as an additional analysis, the difference in cumulative incidence rates between the two

Trial ID: LP0084-1369	Date: 25-Jul-2017	Version: 2.0 Page 41 of 52
-----------------------	--------------------------	-------------------------------

arms will be estimated and presented together with its 95% confidence interval. A landmark analysis will additionally be performed in order to exclude SCC and other neoplasia reported within the first 8 weeks which are not assumed to be associated with the study treatment. This corresponds to left-truncation of the trial period at 8 weeks, which is otherwise conducted as above. Patients who experience a neoplasia before the 8-week landmark time point are excluded from the landmark analysis.

Trial ID: LP0084-1369	Date: 25-Jul-2017	Version: 2.0 Page 42 of 52
-----------------------	-------------------	-------------------------------

Appendix 2: Definitions of Adverse Events and Serious Adverse Events

Adverse Event Definition

An AE is defined as any untoward medical occurrence in a patient or clinical investigation subject administered a pharmaceutical product and which does not necessarily have a causal relationship with this treatment. An AE can therefore be any unfavourable and unintended sign (including an abnormal laboratory finding), symptom, or disease temporally associated with the use of a medicinal (investigational) product, whether or not related to the medicinal (investigational) product. (ICH Harmonized Tripartite Guideline for Good Clinical Practice, E6 (R1)).

This definition includes:

- accidental injuries, events related to trial procedures, reasons for any unfavourable and unplanned change in medication (drug and/or dose), clinically significant worsening of pre-existing conditions, or reasons for admission to hospital or surgical procedures unless these were planned before enrolment. It also includes AEs commonly observed and AEs anticipated based on the pharmacological effect of the IMP. In addition, any laboratory abnormality assessed as clinically significant by the (sub)investigator must be recorded as an AE.

Serious Adverse Event Definition

An SAE is any untoward medical occurrence that

- results in death
- is life-threatening
- requires inpatient hospitalisation or prolongation of existing hospitalisation. Planned hospitalisation or planned prolonged hospitalisation do not fulfill the criteria for being an SAE but should be documented in the subject's medical record.
- results in persistent or significant disability/incapacity
- is a congenital anomaly/birth defect

or

Trial ID: LP0084-1369	Date: 25-Jul-2017	Version: 2.0 Page 43 of 52
-----------------------	--------------------------	-------------------------------

- is a medically important condition. Events that may not be immediately life-threatening or result in death or hospitalisation but may jeopardise the subject or may require intervention to prevent one of the other outcomes listed in the definition above. Examples are intensive treatment in an emergency room or at home for allergic broncospasm, blood dyscrasias and convulsions that do not result in hospitalization, development of drug dependency or drug abuse.

Trial ID: LP0084-1369	Date: 25-Jul-2017	Version: 2.0 Page 44 of 52
-----------------------	-------------------	-------------------------------

Appendix 3: Classification of Adverse Events

Severity

The *severity* of the AE should be described in terms of mild, moderate or severe according to the (sub)investigator's clinical judgement.

Mild	An AE that is usually transient and may require only minimal treatment or therapeutic intervention. The event does not generally interfere with usual activities of daily living.
Moderate	An AE that is usually alleviated with additional specific therapeutic intervention. The event interferes with usual activities of daily living, causing discomfort but poses no significant or permanent risk of harm to the subject.
Severe	An AE that interrupts usual activities of daily living, or significantly affects clinical status, or may require intensive therapeutic intervention.

If the severity of an AE worsens, a new AE should be recorded.

Causality

The *causal relation* of the AE to the use of the IMP should be described in terms of probable, possible or not related according to the following:

Probably related	
Follows a reasonable temporal sequence from administration of the IMP.
 
Could not be reasonably explained by the subject's clinical state, environmental or toxic factors or other therapies administered to the subject.
 
Follows a known pattern of response to the IMP.
 
Disappears or decreases on cessation or reduction in dose of the IMP.
 
Reappears or worsens upon re-challenge.

Possibly related	
Follows a reasonable temporal sequence from the administration of the IMP.
 
Could also be reasonably explained by the subject's clinical state, environmental or toxic factors or other therapies administered to the subject.
 
Follows a known pattern of response to the IMP.

Not related	Does not follow a reasonable temporal sequence from administration of the IMP.

	
Is better explained by other factors like the subject's clinical state, environmental or toxic factors or other therapies administered to the subject.
 
Does not reappear or worsen upon re-challenge.
 
Does not follow a known pattern of response to the IMP.

--	---

Outcome

The *outcome* of the event should be classified and handled as follows:

Recovered/ resolved	The event has stopped. The stop date of the event must be recorded.
Recovering/ resolving	The subject is clearly recovering from an event. The event is not yet completely resolved.
Not recovered/ not resolved	Event is still ongoing.

Appendix 5: Protocol Amendment History

Amendment 1 (27-Jul-2017)

This amendment is considered to be substantial based on the criteria set forth in Article 10(a) of Directive 2001/20/EC of the European Parliament and the Council of the European Union.

Overall rationale for the amendment

The reason for the amendment is to change the definition of the FAS to include all randomised subjects from the pivotal phase 3 trials. The amendment also addresses requests for changes from the Health Authorities in Europe and US after their review of the protocol.

Note: In the table below, text added to the protocol is written in bold and deleted text has a line through it.

Section number and name	Description of change	Brief rationale
1.1.Approval Statement LEO Pharma A/S	PPD [REDACTED], PhD PPD [REDACTED] [REDACTED] M.Sc	New biostatistician
2 Trial identification	Clinicaltrials.gov identifier: NCT03115476	Include CT.gov identifier
6.1 Trial Design	(see section 8.4.1)	Clarification
6.3 Sample Size	The sample size is determined by the number of subjects who complete Visit 11 in the confirmatory phase 3 trials (LP0084-1193, -1194, -1195, -1196) and are willing to enter the extension protocol and is expected to be around 1080.	Aligned with Section 11.1
7.4 Subject Screening and Enrolment Log	Subject Screening and Enrolment Log	Correction of title of log
8.1 Schedule of Trial Procedures	4) Within treatment area only (SAEs outside treatment are only collected if deemed related to IMP in main trial or	Clarification

Trial ID: LP0084-1369	Date: 25-Jul-2017	Version: 2.0 Page 49 of 52
-----------------------	-------------------	-------------------------------

Table 1	reported elsewhere in the CRF). 5) Early termination only.	
8.3 Concomitant Medication and Procedures	
The sentence: "If visit 1 (...)must be recorded at Visit 1." has been moved to the end of the section.
 
The following should be collected:
 
In addition, Information will be collected regarding concomitant medications (topical or systemic) and procedures used for AEs in the treatment area.
	Clarification
8.4 Adverse Events	
If Visit 1 does not coincide with Visit 11 of the main trial (LP0084-1193, -1194, -1195 and -1196) events in the treatment area for the period between the two visits must be recorded at Visit 28.4.1
 
8.4.1 Adverse Events of Special Interest and other Skin Neoplasia
 
 • A new lesion in the treatment area that has bled on more than 2 occasions. • Any papular lesion that measures more than 0.5 cm in diameter (0.2 inches). • A presumed actinic keratosis that has been treated twice with cryosurgery without resolution. 	Editorial change Delete repeated word and insert Heading 3 Addition of clinical guidelines for when investigators should consider biopsy of a 'suspicious' lesion
9.1 Collection of Adverse Events	SAEs occurring outside the treatment area in the main trial, and considered not related to IMP in these trials, will not be systematically collected. For an overview of which AEs should be collected, see table below.	Clarification of which AEs will be collected

Trial ID: LP0084-1369	Date: 25-Jul-2017	Version: 2.0 Page 50 of 52
-----------------------	-------------------	-------------------------------

	Table 2 Overview of AEs to be Collected note: the new table is not inserted here but can be found in Section 9.1	
9.4.1 Investigator Reporting Responsibilities	Any SAE must be reported to LEO on When reporting SAEs, the (paper) SAE Form – Clinical Trials, must be used, and submitted to LEO within 24 hours of first knowledge	Clarification
11.1 Sample size	The total number of subjects in the trials is around 1200, and assuming 10% drop outs after 14 months, the number of subjects being offered the extension protocol will be around 1080. A total of 1200 subjects were planned be enrolled in the pivotal phase 3 trials (LP0084-1193, -1194, -1195, and - 1196) and randomised 2:1 to the two treatment groups ingenol disoxate gel or vehicle gel. With 800 subjects in the ingenol disoxate treatment group and 400 subjects in the vehicle gel group, an adequate precision of the 3-year plus 2 months incidence rate can be obtained. Assuming a 3-year plus 2 months rate of 4.0%, the upper 95% confidence limit will on average be 5.36% for ingenol disoxate gel and 5.92% for vehicle gel, and assuming a 6.0% rate, the upper 95% confidence limit will on average be 7.65% for ingenol disoxate gel and 8.33% for vehicle gel.	Rationale added

Trial ID: LP0084-1369	Date: 25-Jul-2017	Version: 2.0 Page 51 of 52
-----------------------	-------------------	-------------------------------

11.2 Trial Analysis Sets	All enrolled and eligible randomized subjects from the pivotal phase 3 trials (LP0084-1193, -1194, -1195, -1196) are included in the full analysis set (FAS) and will be analysed for incidence of SCC and other skin neoplasia.	Change definition of FAS
Analysis of Primary Endpoint	
The null hypothesis is that there is no difference in time to first SCC between ingenol disoxate gel and vehicle gel. The hypothesis will be tested against the two-sided alternative that there is a difference between the two treatment groups.
 
The annual and the 3-year and 2 months cumulative incidence of first event of SCC will be calculated for each treatment group (active and vehicle) in main trial using methods of survival analysis in the presence of censoring.
	Specification of the null hypothesis for the primary endpoint
Analysis of Secondary Endpoint	
For the secondary endpoint, the null hypothesis is that there is no difference in time to first SCC or other skin neoplasia between ingenol disoxate gel and vehicle gel. The hypothesis will be tested against the two-sided alternative that there is a difference between the two treatment groups.
	Specification of the null hypothesis for the secondary endpoint
14 Handling of Urgent Safety Measure	LEO must act immediately upon receipt of the urgent safety measure notification in accordance with the internal procedures and national requirements.	Request from MHRA

Trial ID: LP0084-1369	Date: 25-Jul-2017	Version: 2.0 Page 52 of 52
-----------------------	-------------------	-------------------------------

23 References	Reference list revised	There was a disconnect between the footnotes and the references listed in section 23
List of Appendices	Appendix 5: Protocol amendment history

The original protocol was dated 23-Feb-2017 and a protocol amendment was issued 25-Jul-2017. Section 6.3 of the protocol was updated to include how sample size was determined for 1369. Section 11.1 was updated to include a precision estimate of the 3-year plus 2 month event rate of squamous cell carcinoma (SCC) where the 95% upper confidence limits are presented. Section 11.2 was updated to change the definition of the full analysis set from all enrolled and eligible subjects in 1369 to all randomized subjects from the pivotal phase 3 trials (LP0084-1193, -1194, -1195, -1196). Sections 11.3.4 and 11.3.5 were updated to include text specifying their respective null hypotheses. The remaining changes were either administrative or matters that needed further clarification. The change to section 11.2 has an impact on the data selection for the primary and secondary analyses, but does not change the manner in which the analyses are conducted. LEO Pharma decided to stop the trial prematurely and hence less data than expected were collected and analyzed.

6 Trial Analysis Sets

The analysis sets are determined based on the criteria defined in the Clinical Trial Protocol, which was changed from the original protocol dated 23-Feb-2017 to an amended version dated 25-Jul-2017. The analysis sets are defined as in the 4 main trials, and therefore a classification meeting will not take place for this trial.

6.1 Subjects enrolled in to LP0084-1369

A total of 562 subjects consented to and were enrolled into the extension trial LP0084-1369.

6.2 Full Analysis Set

A total of 1243 subjects were randomized in the 4 main trials. A total of 9 subjects withdrew consent prior to first application of investigational medicinal product (IMP). IMP was handed out to all 9 subjects but they returned the IMP unused. For all 9 subjects the decision to withdraw could therefore not have been biased by knowledge of the assigned treatment. The 9 subjects were excluded from the full analysis set (FAS) in alignment with ICH E9.

The remaining 1234 randomized subjects applied IMP and were included in the FAS.

Trial ID: LP0084-1369	Date: 27-May-2018	Version: 1.0 Page 7 of 14
-----------------------	-------------------	------------------------------

6.3 Safety Analysis Set

All 1234 subjects in the FAS applied at least one dose of IMP and had presence or confirmed absence of adverse events (AEs) and thereby had post-baseline safety evaluations available. All 1234 subjects in the FAS are included in the safety analysis set.

6.4 Follow-up Analysis Set

The follow-up analysis set (FUAS) was defined as subjects in the FAS who were still in one of the main trials at visit 7 (week 8) and/or for whom evaluations after visit 7 (week 8) were available. The FUAS consists of 1172 subjects.

A difference between actual and planned treatment was only observed for 1 subject in FAS. The planned treatment was vehicle but the subject was treated with Ingenol Disoxate. The subject was included in FUAS but did not experience an event of SCC or other skin neoplasia.

7 Statistical Analysis

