6.5 Blinding

The phase 3 trials LP0084-1193, -1194, -1195, or -1196 are vehicle controlled and blinded. The blinding will, however, not be maintained during the 2 years of the extension protocol except for the blinding of the adjudication committee members, who evaluate the pathology slides from skin neoplasias in the treatment area.

7 Trial Population and Withdrawal

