9.5 Follow-up for Final Outcome of Adverse Events

During the trial, the investigator should follow up for final outcome on all AEs (including SAEs). Once a subject leaves the clinical trial, the investigator should follow up on the outcome of all non-serious AEs classified as of possible/probable relationship to the investigational product for 2 months or until the final outcome is determined, whichever comes first. SAEs must be followed up until a final outcome has been established, i.e. the follow-up may continue beyond the end of the clinical trial.

10 Trial Product

Not applicable

11 Statistical Methods

Data on skin neoplasia from the 14 months observation time in the confirmatory phase 3 trials LP0084-1193, -1194, -1195, and -1196 will be combined with the data from the present trial.

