11.3.8 General Principles

All significance tests will be two-sided using the 5% significance level. All confidence intervals will be presented with 95% degree of confidence.

An observed-cases approach will be used for tabulations of data by visit (i.e. involving only those subjects who attended each specific visit).

Categorical data will be summarised using the number and percentage of subjects in each category. Continuous data will be summarised using the mean, median, standard deviation (SD), minimum and maximum values.

Trial ID: LP0084-1369	Date: 25-Jul-2017	Version: 2.0 Page 28 of 52
-----------------------	-------------------	-------------------------------

Any changes from the statistical analysis planned in this clinical trial protocol will be described and justified in a protocol amendment/the statistical analysis plan update and/or in the clinical trial report dependent on the type of deviation.

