7.1 Baseline Considerations

7.1.1 Demographics

Demographics will be tabulated for the FAS as well as for subjects enrolled in LP0084-1369. Data will be presented by treatment location (face/chest or scalp) and treatment group within treatment location as well as overall by treatment group (ingenol disoxate versus vehicle). The protocol states that demographics will be presented by treatment group in the main trials and by country. However, from the analysis of the main trials it was found that treatment location is an important factor and therefore it was decided to present data by treatment group and location instead of by country. The demographic data, including age, from the time of randomization will be used. The analyses of demographics will be based on the planned treatment.

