7.2.1 Primary Efficacy Criterion

The primary endpoint will be analysed as described in the clinical trial protocol (CTP).

The proportional hazards model will include planned treatment as explanatory variable, and have the proportional hazards assumptions checked by assessing whether or not the survival functions cross each other. The hazard ratio and corresponding 95% Wald confidence limits will be estimated within the proportional hazards model with planned treatment group as explanatory variable. A likelihood ratio test within the proportional hazards model will be applied for comparison of treatment groups. The results will be presented by treatment location (face/chest or scalp) and treatment group within treatment location as well as overall by treatment group (ingenol disoxate versus vehicle). The analysis will be based on the FAS.

The cumulative incidence rate will be calculated as the number of subjects with one or more events divided by the total observation period across all subjects in the FAS. The lower and upper limits of the 95% confidence interval will be calculated using the following SAS code:

Lower=((cinv(0.025,#subjects*2)/2)/total_obs_period)

Upper = ((cinv(0.975,2*(#subjects+1))/2)/total_obs_period)

The cumulative incidence rate and corresponding 95% confidence interval will also be presented by treatment location (face/chest or scalp) and treatment group within treatment location as well as overall by treatment group (ingenol disoxate versus vehicle).

For the landmark analysis described in the CTP time=0 will be defined as the date of visit 7 (week 8). This analysis will be based on the follow-up analysis set (FUAS) excluding subjects who experience an event prior to visit 7. Subjects in FUAS who do not have a visit 7, will have the date of their visit 7 imputed as the date of their visit 6 (week 4) plus 28 days.

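### The SAP adds a second test, by-location comparisons and a person-time rate to the endpoint analyses, unmarked, when treatment-linked outcome data were accessible

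*SAP*

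**What the plan says.** **Protocol version 2.0 (25-Jul-2017).** Section 11.3.4 sets out, for the primary endpoint, cumulative incidence by survival methods, a proportional hazards model if its assumptions hold, a log-rank test of the two groups, a difference in cumulative incidence, and an 8-week landmark analysis. Only SCCs confirmed by the adjudication committee (IAC) count. Section 11.3.5 applies the same scheme to the secondary endpoint. Neither section mentions a likelihood ratio test, results by location or a person-time rate. Section 11.3.8 sets two-sided 5% for every test and adds: "Any changes from the statistical analysis planned in this clinical trial protocol will be described and justified".

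**What was accessible when the SAP was written.** Section 5 reports the sponsor's early stop: "hence less data than expected were collected and analyzed". Section 6.4 says of one subject: "The planned treatment was vehicle but the subject was treated with Ingenol Disoxate". It then gives that subject's endpoint status: "The subject was included in FUAS but did not experience an event of SCC or other skin neoplasia". Section 7.1.1 says that "from the analysis of the main trials it was found that treatment location is an important factor". The main trials feed the endpoint directly: protocol section 11 combines "Data on skin neoplasia from the 14 months observation time in the confirmatory phase 3 trials" with the extension data. On the extension, protocol 6.5 says: "The blinding will, however, not be maintained during the 2 years of the extension protocol", apart from the IAC.

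**What the SAP adds.** Section 7.2.1 opens by referring the primary analysis to the protocol. It continues: "A likelihood ratio test within the proportional hazards model will be applied for comparison of treatment groups". It presents results by face/chest and scalp as well as overall. It also defines a cumulative incidence rate as subjects with events divided by total observation time. Section 7.2.2 repeats all this for the secondary endpoint.

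**The concern.** An analysis first written down when outcome data can be linked to treatment cannot be shown to keep its nominal 5% error rate. Because section 7.2.1 points to the protocol, a reader of the report would take everything in it as planned in July 2017. Three things follow.

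- The primary null hypothesis has two tests at 5%, log-rank and likelihood ratio, and neither is ranked. If they fall on opposite sides of 0.05, the plan does not say which one decides.
- Treatment comparisons within location can give a nominally significant result in one location. No multiplicity control is stated, and the SAP itself says that main-trial results brought location to the fore.
- A person-time rate carries the name that the protocol uses for a survival-based cumulative incidence, so the two can be confused in the report.

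**Working it through.** **1. The plan's own figures.** The only design calculation is the precision statement in protocol 11.1. With upper limit p + 1.96·√(p(1−p)/n):
- p = 4.0%: n = 800 gives 5.358%; n = 400 gives 5.920% (stated 5.36% and 5.92%).
- p = 6.0%: n = 800 gives 7.646%; n = 400 gives 8.327% (stated 7.65% and 8.33%).

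All four agree. The protocol gives no power or event target, so event numbers below are assumptions. The SAP counts also agree: 1243 − 9 = 1234.

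**2. Protocol and SAP side by side, endpoint analyses.**

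| Item | Protocol 11.3.4-11.3.5 | SAP 7.2-7.2.2 | Marked as a change? |
|---|---|---|---|
| Test of treatment | Log-rank | Protocol by reference, plus likelihood ratio test | No |
| Grouping | Two treatment groups | Overall and within two locations | No (explained only for demographics, 7.1.1) |
| Incidence measure | Cumulative incidence, survival methods | Subjects with events / observation time | No |
| Event | IAC-confirmed | MedDRA coding of the AE; IAC not mentioned | No |
| Landmark at 8 weeks | Yes | Yes, in the follow-up analysis set | Method already in protocol |

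**3. Can the two tests of the primary hypothesis disagree?** Under the null with 2:1 allocation, treat the number x of E events on active as binomial with probability 2/3. This approximates the log-rank test by the score statistic.
- Score: (x − 2E/3)² / (2E/9).
- Likelihood ratio: 2[x·ln(x/(2E/3)) + (E−x)·ln((E−x)/(E/3))].

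Take E = 30 and x = 25. The score statistic is 25/6.667 = 3.75, p = 0.053. The likelihood ratio statistic is 2[25·ln(1.25) + 5·ln(0.5)] = 4.23, p = 0.040. They can therefore disagree.

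**4. Chance of p<0.05 with no true effect.** Exact enumeration; one endpoint, time counted from Visit 2; events assumed split equally by location.

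| Events | Overall log-rank | Log-rank or likelihood ratio, overall | Likelihood ratio: overall or either location | Any SAP-added test* |
|---|---|---|---|---|
| 20 | 5.5% | 5.5% | 9.9% | 9.9% |
| 30 | 3.1% | 5.4% | 12.0% | 12.0% |
| 40 | 4.3% | 4.3% | 12.0% | 12.0% |
| 50 | 5.1% | 5.1% | 8.8% | 12.8% |
| 75 | 3.7% | 5.1% | 11.0% | 12.7% |

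*Overall likelihood ratio, or either test within a location.

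Allowing the second overall test leaves the error rate between 4.3% and 5.5%. The rise to about 10-13% comes with the location tests.

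**5. Across the whole set.** Two endpoints × two time origins × three groupings make 12 likelihood ratio tests. If they were independent, 1 − 0.95¹² = 46.0%. They are strongly correlated, so the true figure is lower, and 46.0% serves only as a ceiling.

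**The case against.** **Access is not knowledge of results.** The documents link treatment and outcome for one subject, who had no event. Section 7.1.1 does not say which main-trial outcome or time point made location important. Section 7.4.1 speaks of events as still expected, and the past tense in section 5 is thin evidence on its own. A reader might infer that the author had seen SCC by arm and chose tests accordingly; the documents do not support that. Nor does their silence on lock or unblinding dates prove anything, since part of the SAP text is not in the version available. This objection stands, and the point is limited to accessible data.

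**The SAP does disclose changes.** It explains replacing country by location for demographics (7.1.1), dropping AE tests (7.3.1) and excluding nine subjects from the FAS (6.2). It says that the analysis sets follow the main trials. It would be wrong to say that it hides its changes generally. The undeclared items are those in the endpoint analyses.

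**Location is a design feature.** Face/chest and scalp were separate trials with different concentrations, and protocol 11.3.2 lists location as a baseline characteristic. That is a good reason to show results by location. It does not make treatment comparisons within location prespecified.

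**The other two additions do little to error rates.** The likelihood ratio test sits in a model that the protocol already plans, and step 4 shows that it adds little. The person-time rate has a confidence interval and no p-value, and Appendix I still lists Kaplan-Meier curves. Both points stand. What remains is the lack of ranking and the shared name.

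**Person-time.** A reader might infer that most outcome data were already unblinded because the main trials supply most follow-up. Assume 62 subjects lost before Week 8 (1234 − 1172), about 60 more before Month 14, and 562 entrants averaging 3.5 to 9.5 extension months. The main trials then give about 1,342 person-years against 562 × 3.5/12 = 164 to 562 × 9.5/12 = 445, a share of 89% to 75%. That is a share of assumed person-time. It measures neither events seen by arm nor bias.

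**The report.** Protocol 11.3.8 also allows changes to be described in the clinical trial report, which is not available here. That offers a second place for the correction, but section 7.2.1 would still present the additions as the protocol's analysis.

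**Conclusion.** The point holds as a matter of labelling and ranking. Three items entered the primary and secondary endpoint analyses in a SAP written after the early stop, with treatment-linked outcome data accessible, under a sentence that refers back to the protocol. They are not described or justified as changes. The illustrative cost is a 10-13% chance of at least one p<0.05 among SAP-added tests, for one endpoint and one time origin, against 3.1-5.5% for the overall log-rank test alone. The range rests on assumed event numbers (20 to 75) and an assumed equal split by location.

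Two stronger readings should be resisted. One is that only the overall log-rank test is prespecified. The secondary-endpoint comparison, the proportional hazards model and the landmark analysis are all in the July 2017 protocol and keep that status as methods. The other is that the overall log-rank result is safe as it stands. The SAP defines its events by MedDRA preferred term, whereas the protocol requires IAC confirmation, so that difference must be settled before the result is called prespecified.

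**What to change.** In SAP 7.2.1, and by reference in 7.2.2:

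1. Name the protocol's overall log-rank test in the FAS as the test of the primary hypothesis.
2. Keep the protocol's secondary-endpoint, proportional hazards and landmark analyses as prespecified.
3. Label the likelihood ratio test and the within-location comparisons as added in the SAP and exploratory, with nominal p-values or none.
4. List the person-time rate as a SAP addition under its own name, and state that it does not replace the survival-based cumulative incidence.
5. State which data were accessible, linked to treatment, when the SAP was signed.
6. Reconcile the event definition in SAP 7.2 with the IAC confirmation in protocol 11.3.4-11.3.5.

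Carry the labels into the clinical trial report. If a document dated before data access already specified an added item, cite it and the exploratory label can go. Items 1 to 5 change wording only. Item 6 may change which events enter the analysis if the two definitions give different sets. The price is that the added analyses can no longer be reported as planned.
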